### **6.3 DISCONTINUATION OF PATIENTS FROM THERAPY OR ASSESSMENT**

A premature discontinuation will occur when a patient who signed the ICF ceases participation in the trial, regardless of circumstances, before the completion of the protocol. Patients can prematurely discontinue or be prematurely discontinued by the investigator or Sponsor from the trial at any time for any reason including the following:

- Failure to meet Inclusion/Exclusion Criteria (Screening or Pretreatment Failure)
- Adverse event (AE)
- Lack of efficacy
- Protocol violation
- Non-compliance with study drug
- Withdrawal of consent
- Lost to follow-up (every effort must be made to contact the patient; a certified letter must be sent)
- Trial termination by Sponsor
- Pregnancy
- Other, such as administrative reasons

Patients who are randomized but do not complete the Treatment Period or RW Period (withdraw consent or are discontinued before they have completed 12 weeks or 4 weeks of treatment, respectively) will be considered Treatment Period or RW Period withdrawals, respectively, and should complete the procedures required at the Week 16/EOT Visit (even if out of window) at the time of their discontinuation. The reasons for premature discontinuation from the trial will be documented on the study termination form of the eCRF. All data on the patient prior to discontinuation will be made available to Ironwood (or designee). Any patient who withdraws because of an AE will be followed until the AE resolves, stabilizes, or can be explained as being unrelated to study drug. The trial centers should make a reasonable effort to follow pregnant patients until delivery or end of the pregnancy.

If a patient does not return for a scheduled termination visit (EOT Visit), the trial center should contact the patient. Every effort is to be made to contact the patient, including sending a certified letter. In every case, the patient outcome, including lost to follow-up information, will be documented.

The investigator may allow a patient to stop taking study drug for up to 3 days should an intolerable AE occur. If the investigator believes that the patient is unable to resume dosing or requires a suspension of dosing on more than one occasion, the investigator should contact the Medical Monitor to discuss the patient's continued participation in the trial.

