### Treatment-emergent Adverse Event

A treatment-emergent AE (TEAE) is an event that emerges, or a preexisting event that worsens, any time after administration of the first dose of study drug (Day 1).

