### **8.2.1.3 Procedures for Recording Adverse Events**

The investigator will record all AEs from the time informed consent is obtained until completion of trial participation (eg, early termination or Week 16/EOT Visit). At each trial visit, the investigator will inquire about the occurrence of AEs/SAEs since the last visit.

The occurrence of an AE or SAE may come to the attention of trial center personnel during trial visits and interviews of a trial patient presenting for medical care, or upon review by a site monitor. All AEs including SAEs will be captured on the appropriate eCRF. Information to be collected includes event description, time of onset, clinician's assessment of severity, relationship to study drug (assessed only by those with the training and authority to make a diagnosis), and time of resolution/stabilization of the event. All AEs occurring while on study must be documented appropriately regardless of relationship. All AEs will be followed to adequate resolution or stabilization.

Any medical condition that is present at the time that the patient is screened and does not deteriorate (worsen in severity and/or frequency) should be recorded as Medical History and not as an AE. However, if the patient's condition deteriorates at any time during the trial, it will be recorded as an AE. AEs characterized as intermittent require documentation of onset and duration of each episode.

Pretreatment AEs will be collected and captured in the patient's source documentation from the time the patient signs the ICF until the patient receives study drug. Pretreatment AEs in randomized patients will additionally be entered on the AE page of the patient's eCRF.

Laboratory abnormalities, changes in vital signs, and physical examination findings should be considered AEs and reported on the AE page of the patient's eCRF only if the investigator considers them clinically significant and/or they necessitate intervention.

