### **10.6.1               Adverse Events**

Adverse Event Verbatim Terms will be coded in the EDC system against the most current version of MedDRA available at the start of the trial (or newer).

An AE that occurs during the Treatment Period will be considered a treatment-emergent AE (TEAE) for the Treatment Period if it was not present prior to the date of the first dose of double-

blind study drug, or was present prior to the date of the first dose but increased in severity during the Treatment Period.

Similarly, an AE that occurs on or after the date of the first dose of double-blind study drug for the RW Period (up to 1 day after the last dose of double-blind study drug) will be considered a TEAE for the RW Period if it was not present prior to the date of first dose of study drug for the Treatment Period, or was present prior to the date of the first dose for the Treatment Period but increased in severity on or after the date of the first dose for the RW Period.

An AE that occurs on or after the date of the first day of dosing in the RW Period (up to 1 day after the last dose of double-blind study drug) will be considered a newly-emergent adverse event (NEAE) for the RW Period if it was not present prior to the date of the first calendar day of dosing in the RW Period, or was present prior to the date of the first calendar day of dosing in the RW Period, but increased in severity on or after the date of the first calendar day of dosing in the RW Period.

If more than one AE is reported prior to the first dose of double-blind study drug and coded to the same preferred term, the AE with the greatest severity will be used as the benchmark for comparison with the AEs occurring during the Treatment and RW Periods that were also coded to that preferred term. An AE that occurs more than 1 day after the last dose of double-blind study drug will not be counted as a TEAE or NEAE.

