For the Treatment and RW Periods, the number and percentage of patients reporting TEAEs in each treatment group and treatment sequence, respectively, will be tabulated by system organ class (SOC) and preferred term; by SOC, preferred term, and severity; and by SOC, preferred term, and relationship to study drug. If a patient has more than one TEAE coded to the same preferred term, the patient will be counted only once for that preferred term by identifying those TEAEs with the highest severity and the closest relationship to study drug. Similar tabulations will be presented for the number and percentage of patients reporting NEAEs in the RW Period by treatment sequence.

The distribution of TEAEs by severity and relationship to study drug will be summarized by treatment group for the Treatment Period. Similarly, the distribution of TEAEs and NAEs by severity and relationship to study drug will be summarized by treatment sequence for the RW Period.

The incidence of common TEAEs, on-therapy SAEs, and AEs leading to premature discontinuation of study drug will be summarized by preferred term and treatment group for the Treatment Period and treatment sequence for the RW Period. In addition, the incidence of fatal SAEs (ie, events that caused death), if any, will be summarized separately by treatment group for the Treatment Period and treatment sequence for the RW Period, and preferred term.

Listings will be presented for patients with SAEs, patients with AEs leading to discontinuation, and patients who die (if any).

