#### **7.11.1            *Adverse Events***

Adverse events will be coded by system organ class and preferred term using the MedDRA dictionary, version 21.0.

An AE that occurs during the Treatment Period will be considered a treatment-emergent adverse event (TEAE) if it was not present prior to the date of the first dose of double-blind study drug or was present prior to the date of the first dose but increased in severity during the Treatment Period. If more than 1 AE was reported before the first dose of double-blind study drug and coded to the same preferred term, the AE with the greatest severity will be used as the benchmark for comparison with the AEs occurring during the Treatment Period that were also coded to that preferred term.

An AE that occurs on or after the date of the first dose of the double-blind study drug for the RW Period will be considered a TEAE for the RW Period (RW TEAE) if it was not present prior to the date of the first dose of double-blind study drug of the Treatment Period or was present prior to the date of the first dose of double-blind study drug for the Treatment Period but increased in severity on or after the date of the first dose of the double-blind study drug for the RW Period. An AE that occurs more than 1 day after the last dose of study drug in the RW Period will not be considered a RW TEAE.

An AE that occurs on or after the date of the first dose of the double-blind study drug for the RW Period will be considered a newly emergent adverse event (NEAE) for the RW Period if it was not present prior to the date of the first dose of the double-blind study drug for the RW Period or was present prior but increased in severity after receiving RW period double-blind study drug. An AE that occurs more than 1 day after the last dose of double-blind study drug will not be counted as an NEAE.

The period in which a serious adverse event (SAE) occurred will follow the methods defined above for TEAEs, RW TEAEs, and NEAEs. [Table 7.11-1](#) summarizes the classification of AEs.

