**Table 7.11-1 Adverse Event Classification**

Type of AE	Reference Period for Baseline	Starting Point of Period	Ending Point
TEAE	Screening+ pretreatment	First dose during treatment period	Earlier of day after last dose of Trt period & day before first dose of RW period
RW TEAE	Screening+ pretreatment	First dose during RW period	Day after date of last dose of RW trt
NEAE	Screening+ pretreatment+ treatment	First dose during RW period	Day after date of last dose of RW trt

The number and percentage of patients in each treatment group who experience TEAEs will be summarized. For the Treatment Period, TEAEs will be summarized for each treatment group by system organ class and preferred term; by system organ class, preferred term, and severity; and by system organ class, preferred term, and relationship to study drug. The same summaries will be provided for each treatment sequence for the RW Period (RW TEAEs and NEAEs). For the Treatment-RW Period, TEAEs will be summarized for each treatment sequence by system organ class and preferred term only. If a patient has more than 1 AE coded to the same preferred term, the patient will be counted only once for that preferred term by identifying those TEAEs with the greatest severity and the closest relationship to study drug for the summarization by severity and by relationship to the study drug, respectively.

For the Treatment Period, the incidence of common ( $\geq 2\%$  of patients in any treatment group) TEAEs, on-therapy serious adverse events (SAEs), and AEs leading to premature discontinuation of study drug will be summarized by preferred term and treatment group, sorted in decreasing frequency. The above summaries will also be provided for the RW Period by treatment sequence. In addition, the incidence of on-therapy SAEs that led to death will be summarized.

For the Screened Population, listings will be presented for patients who died, patients with SAEs, and patients with AEs leading to premature discontinuation, if any.

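### AE incidence tables stop one day after the last dose although AEs are collected to the last visit, and the SAP limits the fatal-SAE summary to on-therapy events where the protocol does not

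*Protocol*

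**What the plan says.** **Collection.** Under protocol Section 8.2.1.3 the investigator will "record all AEs from the time informed consent is obtained until completion of trial participation", which means early termination or the Week 16/EOT Visit. Section 6.3 asks patients who stop early to complete the EOT procedures, and patients who withdraw for an AE are followed further.

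**Counting.** Protocol Section 10.6.1 states that an "AE that occurs more than 1 day after the last dose of double-blind study drug will not be counted as a TEAE or NEAE". SAP Table 7.11-1 ends the Treatment Period window at the "Earlier of day after last dose of Trt period & day before first dose of RW period" and the RW windows on the day after the last RW dose. For SAEs the SAP adds: "The period in which a serious adverse event (SAE) occurred will follow the methods defined above for TEAEs, RW TEAEs, and NEAEs".

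**A second definition.** Protocol Section 8.2.1.1 describes a TEAE as one that emerges or worsens "any time after administration of the first dose of study drug (Day 1"), with no end point.

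**Pauses.** Protocol Section 6.3: "The investigator may allow a patient to stop taking study drug for up to 3 days should an intolerable AE occur". Neither document says how the counting window treats a pause.

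**Fatal SAEs.** Protocol Section 10.6.1: "the incidence of fatal SAEs (ie, events that caused death), if any, will be summarized separately", by group for the Treatment Period and by sequence for the RW Period. The SAP text below Table 7.11-1 says instead: "the incidence of on-therapy SAEs that led to death will be summarized".

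**Listings.** Both documents plan listings of SAEs, deaths and AEs leading to discontinuation. No on-therapy limit is stated for them.

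**The concern.** The end of collection and the end of counting differ, and no reason is given for choosing one day. The gap matters most for patients who stop early. A new event that follows the stop by two days or more is in the database but in no incidence table that these documents describe.

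A pause makes the rule depend on what happens later. Two patients with the same event on the same off-drug day are treated differently according to whether they go back on drug, and the one who could not resume loses the event from the count.

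For fatal SAEs the SAP is narrower than the protocol it implements. Safety is analysed descriptively, so no hypothesis test is affected. What is at stake is whether the incidence tables give a complete account of events after stopping, and whether the fatal-SAE summary is the one the protocol describes.

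**Working it through.** No figure in the plan depends on this window, so there is none to reproduce. The check consists of calendar arithmetic, the protocol's discontinuation rates, and a comparison of wording.

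**1. Pause.** Rule: an onset counts if onset day ≤ last dose day + 1. Take a last dose on Day 20 and a pause on Days 21 to 23.

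| Onset | Dosing resumes | Dosing never resumes (cut-off 20 + 1 = Day 21) |
|---|---|---|
| Day 21 | counted | counted |
| Day 22 | counted | not counted |
| Day 23 | counted | not counted |

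**2. Collected but uncounted days.** If the termination visit falls k days after the last dose, the gap is max(0, k − 1) days.

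- k = 1 gives 0 days, k = 3 gives 2, k = 7 gives 6, and k = 14 gives 13. Section 6.3 sets no maximum for k.
- For completers, a last dose on RW Day 28 and a visit on RW Day 32 (29 + 3) leave RW Days 30 to 32, or 3 days. Dosing through RW Day 31 leaves none.

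**3. Arm imbalance in diarrhea stops.** The rates come from protocol Section 3.3, with 300 patients per arm from Section 10.8.

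- Phase 3 rates: 300 × 5.3% = 15.9 on linaclotide; 300 × 0.4% = 1.2 on placebo. The ratio is 5.3 / 0.4 = 13.25.
- Phase 2b rates: 300 × 6.1% = 18.3 on linaclotide; 300 × 0% = 0 on placebo.

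**4. Patients with an uncounted onset.** The documents do not give the share q of these patients who have a new event after last dose + 1 day and before the last visit. The table assumes q from 5% to 50% for illustration; prompt termination visits would push q towards zero.

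| Rates | Linaclotide, patients | Linaclotide, points | Placebo, patients | Placebo, points |
|---|---|---|---|---|
| Phase 3 | 15.9 × 0.05 to 0.50 = 0.8 to 8.0 | 0.27 to 2.65 | 1.2 × 0.05 to 0.50 = 0.06 to 0.6 | 0.02 to 0.2 |
| Phase 2b | 18.3 × 0.05 to 0.50 = 0.9 to 9.2 | 0.3 to 3.05 | 0 | 0 |

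At Phase 3 rates, q = 100% would give 5.3 against 0.4 points. These are patients with at least one uncounted onset. Most would still count in an overall TEAE total because of the diarrhea that led them to stop.

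**5. Wording on SAEs.** Protocol Section 10.6.1 limits its general SAE summary to on-therapy events, and the SAP does the same, so these agree. For fatal SAEs the protocol names no such limit and the SAP does. Neither document defines on-therapy; reading it as the TEAE-type windows rests on the SAP sentence that gives SAEs those windows.

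**The case against.** A short on-treatment window is a defensible attribution rule for a drug that protocol Section 3.2 describes as minimally absorbed. It was prespecified, and the SAP follows it. The AE that causes a stop normally begins on drug and is counted, and AEs leading to discontinuation have their own summary. Each patient counts once per preferred term, so recurrence of the same event at no greater severity changes nothing. Section 6.3 places the EOT procedures at the time of discontinuation, so the gap may be close to zero. Specifications of tables and listings are in a separate document, so late non-serious events may be listed there. All of this stands, and it keeps the point modest. It does not explain why counting should turn on resumption, or why the fatal-SAE summary was narrowed.

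A reader might infer more than the documents support:

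- *That SAE incidence in general falls short of the protocol.* It does not; the on-therapy limit on the general SAE summary is already in Section 10.6.1.
- *That the protocol commits to fatal SAEs from first dose to the EOT visit.* It states no such window; it organises the summary by period and omits the on-therapy limit.
- *That early stopping as a whole is concentrated on linaclotide.* Section 3.3 gives rates for diarrhea stops only, with no all-cause rate by arm. Stops for lack of efficacy, withdrawn consent or loss to follow-up shorten the window on placebo in the same way.
- *That the TEAE window should be lengthened for early stoppers.* That would give them more off-drug observation time than completers, by an amount that varies with the visit date.

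**Conclusion.** The point holds in limited form. New-onset events from the second day after the last dose are collected but left out of the TEAE, NEAE and on-therapy SAE tables. Counting of an event during a permitted pause depends on resumption. The SAP's fatal-SAE summary carries a limit that the protocol's does not, and the protocol's two TEAE definitions disagree on whether there is an end point.

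The effect is probably small, and its size cannot be fixed from the documents. The one documented imbalance is in diarrhea stops, about 16 to 18 against 0 to 1 per 300, and that assumes the earlier trials' rates apply here. Any count of uncounted events rests on an assumed share and on the unstated interval between last dose and termination visit. The text does not support saying that these events vanish from the report, since late SAEs, deaths and AEs leading to discontinuation are listed.

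**What to change.** Keep the last dose + 1 day TEAE table as the main display. In SAP Section 7.11.1:

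1. Summarize fatal SAEs without the on-therapy restriction, as protocol Section 10.6.1 does.
2. Add supportive tables of all SAEs and all AEs from first dose through the last visit, under the same rule for every patient in both arms, with on-therapy onset flagged. Retain the split by treatment group for the Treatment Period and by sequence for the RW Period.
3. Define on-therapy, and state how a dosing pause is handled when the end of the counting window is derived.

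Reconcile the TEAE definitions in protocol Sections 8.2.1.1 and 10.6.1, and the fatal-SAE wording in protocol Section 10.6.1 and the SAP.

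The cost is SAP wording, a date rule and a few extra tables; the data are already collected. The downside is that a few events with onset off drug appear in the supportive tables, where rates will look slightly less favourable.

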#### **10.6.2 Clinical Laboratory Parameters**

Descriptive statistics for clinical laboratory values (in standard units) and changes from the baseline values at each assessment time point will be presented by treatment group for the Treatment Period and by treatment sequence for the Combined Treatment and RW Period, for each clinical laboratory parameter.

The number and percentage of patients with potentially clinically significant (PCS) post-baseline clinical laboratory values will be tabulated by treatment group for the Treatment Period and by treatment sequence for the RW Period and the Combined Treatment and RW Period. The criteria for PCS laboratory values will be detailed in the SAP. The percentages will be calculated relative to the number of patients with available non-PCS baseline values and at least 1 assessment in the corresponding post-baseline period. The numerator will be the total number of patients with available non-PCS baseline values and at least 1 PCS value in the corresponding post-baseline period. A supportive listing of patients with PCS post-baseline values will be provided, including the PID number, trial center, and baseline and post-baseline values. A listing of all AEs for patients with PCS laboratory values will also be provided.

### **10.6.3            Vital Signs**

Descriptive statistics for vital signs (ie, pulse rate, systolic and diastolic BP, respiratory rate, temperature, and body weight) and changes from baseline at each visit and at the end of the period/trial will be presented by treatment group for the Treatment Period and by treatment sequence for the Combined Treatment and RW Period.

The number and percentage of patients with PCS post-baseline vital signs will be tabulated by treatment group for the Treatment Period and by treatment sequence for the Combined Treatment and RW Period. A vital sign value will be considered PCS if it meets both the observed value criterion and the change from baseline value criterion. The criteria for PCS vital sign values will be detailed in the SAP. The percentages will be calculated relative to the number of patients with baseline values and at least 1 assessment in the corresponding post-baseline period. The numerator will be the total number of patients with available non-PCS baseline values and at least 1 PCS value in the corresponding post-baseline period. A supportive listing of patients with PCS post-baseline values will be provided, including the PID number, trial center, and baseline and post-baseline values. A listing of all AEs for patients with PCS vital sign values will also be provided.

### **10.7            INTERIM ANALYSIS**

No interim analysis is planned for this trial.

### **10.8            DETERMINATION OF SAMPLE SIZE**

The sample size of 600 patients (300 patients per treatment group) was chosen to ensure adequate power for testing the fixed-sequence procedure for the primary and secondary efficacy endpoints as defined in Section 10.4.5.

The power calculations for the primary endpoint are based on the placebo and linaclotide 290 µg treatment groups from the Phase 3 trial LIN-MD-31. The patients in LIN-MD-31 are considered representative of the patient population for this trial. Using a resampling with replacement-based simulation (1000 iterations) and controlling for multiplicity as outlined above, the trial will have >99% power to reject the primary endpoint and ~94% power to reject all primary and secondary hypotheses defined in the testing process.

